3.2 Omadacycline

The investigational product, omadacycline (formerly named PTK 0796), is the first member of the aminomethylcycline class of antibiotics, which are semisynthetic derivatives of the

tetracycline class. As a class, tetracyclines have been in use for approximately 70 years. They are well-tolerated and have proven effective in the treatment of a variety of bacterial infections. Intravenous NUZYRA (omadacycline) and oral NUZYRA tablets have been approved by the US FDA for the treatment of adult patients with community-acquired bacterial pneumonia (CABP) and acute bacterial skin and skin structure infections (ABSSSI) caused by susceptible microorganisms.

While data from the completed nonclinical program supports dosing up to 90 days, this is the first clinical trial that will administer study dosing of omadacycline beyond 14 days of therapy. Current-use data indicate that omadacycline is being used for chronic dosing without any safety signal identified, through Paratek's post-marketing pharmacovigilance program and published cases studies. Review of post-marketing off-label use reports did not reveal any trends or recommended updates to the current reference safety information. As of January 2021, 5 case series have been published that together report experience on 19 patients with NTM infections, predominately *M. abscessus* ([Frizzell 2020](#); [Gill 2019](#); [Minhas 2019](#); [Morissette 2021](#); [Pearson 2020](#)). Patients were treated with oral omadacycline for periods ranging from 4 weeks to 20.6 months, all but one as part of a multidrug regimen. Omadacycline was overall safe and well-tolerated. Clinical success was reported in 16 patients. Reported events were consistent with the established safety profile and are not unexpected. These real-world observational reports of treatment with omadacycline for NTM provide support to progress to a randomized controlled trial setting, including long-term dosing.

Please refer to the current version of the [Investigator's Brochure](#) for additional information on omadacycline.

3.3 Properties of Omadacycline that Address the Unmet Treatment Need for *M. abscessus* Complex Pulmonary Infection

Omadacycline has several key characteristics that may prove beneficial to patients with MABC pulmonary infection:

- Potent in vitro activity versus *M. abscessus* complex subspecies

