8.19.3 Assessment of Severity

The severity (or intensity) of an AE will be classified using the following criteria:

- Mild: These events are usually transient, require minimal or no treatment, and do not interfere with the subject's daily activities.
- Moderate: These events result in a low level of inconvenience or concern with the therapeutic measures. Moderate events may cause some interference with normal functioning but pose no significant or permanent risk of harm.
- Severe: These events interrupt a subject's usual daily activity and may require systemic drug therapy or other treatment. Severe events are usually incapacitating.

Changes in the severity of an AE should be documented as a new event to allow an assessment of the duration of the event at each level of intensity to be performed.

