6. GENERAL ANALYSIS CONSIDERATIONS

The statistical analyses will be reported using summary tables, listings, and figures (TLFs). The International Council for Harmonisation of Technical Requirements for Pharmaceuticals for Human Use (ICH) numbering convention will be used for all TLFs. Unless otherwise noted, all p-values will be 2-sided. No adjustments for multiplicity will be made in this study, and any p-values presented are not testing pre-specified inferential hypotheses.

Continuous variables will be summarized by presenting the number of observations, means, SDs, medians, minimums, and maximums. Other summaries (e.g., quartiles, 5%, 95% CIs) may be used as appropriate.

Categorical variables will be summarized by presenting counts and percentages of subjects in corresponding categories. All possible categories as defined in the eCRF should be populated, even if they have zero counts. Percentages are based on the total number of subjects (N) for a given treatment and population, unless otherwise specified.

All summary tables will be presented by treatment group. Baseline summaries will also include a total summary column.

Individual subject data obtained from the eCRFs, external vendors, central clinical laboratory, central electrocardiogram (ECG) laboratory, and selected derived data will be presented by subject in data listings.

The analyses described in this plan are considered a priori, in that they have been defined before breaking the blind.

Any analyses performed after breaking the blind will be considered post hoc and exploratory. Post hoc analyses will be labeled as such on the output and identified in the CSR.

All analyses and tabulations will be performed using SAS® statistical software, version 9.4 or higher (SAS Institute Inc). TLFs will be presented in rich text format (RTF) and/or PDF.

The process for SAS program validation and quality control (QC) for programs and outputs is documented in the Synteract working instruction “SAS Programming Quality Control”. Study-specific QC requirements can be found in APPENDIX B: SAS PROGRAMMING QUALITY CONTROL REQUIREMENTS.

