8. ANALYSIS SETS

The following subject population will be used for safety analyses:

- The safety analysis set will include all subjects who received at least 1 dose of test article. Treatment assignment will be based on the actual test article received the majority of time while on treatment.

The following subject populations will be used for efficacy analyses:

- The intent-to-treat (ITT) analysis set will include all randomized subjects. Treatment assignment will be based on the randomized treatment.
- The per-protocol (PP) analysis set will include all randomized subjects who received at least 1 dose of test article and completed the study without major protocol deviations that affect the assessment of efficacy. The decision whether a subject is excluded from the PP analysis set will be made prior to database lock and unblinding. Treatment assignment will be based on randomized treatment.

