13. SAFETY ANALYSES

All safety analyses will be based on the safety analysis set.

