13.2 Adverse Events

All AE summaries will be restricted to treatment-emergent AEs (TEAEs), which are defined as those AEs that occurred on or after first dose of test article and those existing AEs that worsened on or after first dose of test article. If it cannot be determined whether the AE is treatment emergent due to a partial onset date, then it will be counted as such. Verbatim terms in the eCRFs will be mapped to SOCs and PTs using MedDRA, version 24.0.

Each AE summary will be displayed by treatment group. Summaries that are displayed by SOC and PTs will be ordered by descending subject count in the total column by SOC and PT. Summaries of the following types will be presented:

- Overall summary of AEs that contains an overview of each of the following points
- Subject incidence of TEAEs and total number of unique TEAEs by MedDRA SOC and PT
- Subject incidence of TEAEs by MedDRA PT shown in order of descending frequency of PT in the omadacycline group
- Subject incidence of TEAEs by MedDRA SOC, PT, and highest severity. At each level of subject summarization, a subject is classified according to the highest severity if the subject reported 1 or more events. Adverse events with missing severity will be considered severe for this summary.
- Subject incidence of TEAEs by MedDRA SOC, PT, and closest relationship to test article (related/not related) as classified by the principal investigator. At each level of subject summarization, a subject is classified according to the closest relationship if the subject reported 1 or more events. Adverse events with a missing relationship will be considered related for this summary.
- Subject incidence of serious TEAEs and total number of unique serious TEAEs by MedDRA SOC and PT
- Subject incidence of TEAEs resulting in death by MedDRA SOC and PT

- Subject incidence of TEAEs leading to test article discontinuation by MedDRA SOC and PT
- Subject incidence of TEAEs leading to study discontinuation by MedDRA SOC and PT
- Subject incidence of TEAEs that occurred with onset date up through Day 15 by MedDRA SOC and PT
- Subject incidence of TEAEs that occurred with onset date after Day 15 by MedDRA SOC and PT

A summary of TEAEs experienced by treatment arm by PT will be provided.

Separate listings of serious AEs (SAEs), AEs resulting in death, AEs leading to test article discontinuation, and AEs leading to study discontinuation will be provided.

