- Legends will be used for all figures with more than 1 variable or item displayed. Treatment group sizes (n=xx) will be included, as appropriate.
- Figures will be in black and white but can be in color to add value to the clarity and readability of a figure. Lines must be wide enough to see the line after being copied.
- The last footnotes will be:
 - “Source: xxx”, where xxx indicates the source listing number(s) and/or source dataset(s) (e.g., ADaM).
 - “PROGRAM SOURCE: ...\\xx.sas, DATA CUTOFF DATE: DD Mmm YYYY, RUN DATE: DD Mmm YYYY hh:mm”.
- Line graphs over time of change from baseline results will include a horizontal dashed reference line at zero.

Listings

- If not otherwise specified, all data listings will be sorted by subject number, treatment, visit, and date/time, as appropriate.
- All date values will be presented in a SAS® statistical software, version 9.4 or higher (SAS Institute Inc) date format (e.g., 29AUG2001).
- All observed time values will be presented using a 24-hour clock format (HH:MM:SS) (e.g., 01:35:45 or 11:26). Seconds will only be reported if they were measured as part of the study.
- The last footnote will be “PROGRAM SOURCE: ...\\xx.sas, DATA CUTOFF DATE: DD Mmm YYYY, RUN DATE: DD Mmm YYYY hh:mm”.

Missing or Incomplete Dates

Adverse Events and Concomitant Medications

The most conservative approach will be systematically considered. If the adverse event (AE) onset date is missing/incomplete, it is assumed to have occurred during the study treatment phase (i.e., considered a treatment-emergent AE) except if the partial onset date or other data, such as the stop date, indicates differently. Similarly, a medication with partial start and stop dates could be considered as both a prior and concomitant medication.

The following algorithms will be applied to missing and incomplete start and stop dates:

Start Dates

- If the day portion of the start date is missing, then the start date will be estimated to be equal to the date of the first dose of test article, provided the start month and year are the same as the date of the first dose of test article and stop date is either after the date of the first dose of test article or completely missing. Otherwise, the missing day portion will be estimated as "01."

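### The after-Day-15 adverse event table counts an early event that merely eases later as late onset, because each severity change is a new record and the SAP sorts by onset date alone

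*SAP*

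**What the plan says.** Recording. Protocol section 8.19.3 instructs sites: "Changes in the severity of an AE should be documented as a new event". The stated purpose is to measure how long an event lasts at each intensity, so each record needs its own start date. The instruction makes no exception for improvement.

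Analysis. The TEAE definition in SAP section 13.2 takes in "those AEs that occurred on or after first dose of test article and those existing AEs that worsened on or after first dose". The section then lists two summaries split by time: one for onset up through Day 15, and "Subject incidence of TEAEs that occurred with onset date after Day 15 by MedDRA SOC and PT". The SAP says how several records for one subject are resolved in the severity table (highest grade) and in the relationship table (closest relationship). It gives no such rule for the two Day 15 tables.

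Denominator. SAP section 13: "All safety analyses will be based on the safety analysis set". SAP section 8: "The safety analysis set will include all subjects who received at least 1 dose of test article". SAP section 6: "Percentages are based on the total number of subjects (N) for a given treatment and population, unless otherwise specified". Nothing else is specified for the Day 15 tables, so full N applies.

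Partial dates. Under SAP Appendix A, if the onset day is missing and the month is that of the first dose, "then the start date will be estimated to be equal to the date of the first dose of test article", subject to a condition on the stop date. Otherwise the day is set to the 1st of the month.

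Context. Protocol section 3.2 states that "this is the first clinical trial that will administer study dosing of omadacycline beyond 14 days of therapy", and section 3.3 describes the earlier Phase 3 safety base as covering up to 14 days.

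**The concern.** Safety is a primary objective, and no data monitoring committee is planned. The Day 15 pair is the only adverse event summary that separates the duration already studied in trials from the duration that is new here. The SAP does not say why it cuts at Day 15, but the match with 14 days makes the purpose a fair inference.

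If the protocol's recording rule and the SAP's sorting rule are both followed as written, the tail of an early event appears as late onset. A reader of the late table could then take the gradual resolution of early intolerance for toxicity that emerges with longer dosing. The table does not separate three situations: a new event, an earlier event getting worse, and an earlier event getting better.

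**Working it through.** The plan states no figure for these tables, so there is none to reproduce. Its power figure (about 80%) plays no part here; only the planned arm sizes, 45 and 30, are used.

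**1. The two rules applied to one subject.** Nausea is moderate from Day 3, eases to mild on Day 20 and resolves on Day 30.

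| Record | Severity | Onset | Table |
|---|---|---|---|
| 1 | moderate | Day 3 | up through Day 15 |
| 2 | mild | Day 20 | after Day 15 |

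The subject counts in both tables, although nothing new began after Day 15.

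**2. Size.** Let p be the share of an arm with a given preferred term starting by Day 15, and q the share of those whose grade changes after Day 15. The share entering the late table through a grade change is at most p × q. The documents give neither p nor q, so the values below are assumptions.

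| p | q | p × q | of 45 on omadacycline |
|---|---|---|---|
| 10% | 10% | 1.0% | 0.45 |
| 20% | 25% | 5.0% | 2.25 |
| 30% | 50% | 15.0% | 6.75 |

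These are upper bounds for two reasons. Some of these subjects may also have a true late onset of the same term. And q includes increases in severity, which are real late findings; only decreases are spurious.

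**3. What full N does.** A completer (last dose Day 84) has 84 − 15 = 69 days on drug after Day 15. Follow-up is 30 to 37 days after the last dose, so observation after Day 15 lasts 99 to 106 days. A subject whose last dose is Day 10 is followed to Day 40 to 47, which is 25 to 32 days after Day 15, all off drug. Such a subject is observed for late events but not exposed to longer dosing.

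Suppose 2, 4, 7 or 9 of 45 subjects stop by Day 15 (about 5% to 20%, assumed) and have no later events. The full-N percentage is then 43/45 = 0.96, 41/45 = 0.91, 38/45 = 0.84 or 36/45 = 0.80 of the percentage among those still dosing. With a 20% late rate in those still dosing and 7 stoppers, the table shows 38 × 0.20 / 45 = 16.9%. If the stoppers have late events at half that rate, it shows (7.6 + 0.7)/45 = 18.4%. The dilution depends on what stoppers experience off drug.

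**4. Partial dates.** With first dose on 20 January (Day 1), 1 February is Day 13, 3 February is Day 15 and 25 February is Day 37. A true onset on 25 February recorded without its day becomes 1 February, hence early. Yet 25 of the 28 days of that February (4th to 28th) fall after Day 15. The first-dose rule has the same effect when dosing starts early in a month: with first dose on 2 January, a January onset without a day becomes Day 1, although 17 to 31 January fall after Day 15.

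**The case against.** The strongest reply is that the mock tables, the dataset specifications and the annotated eCRF are separate documents, not available here, and may contain a linking rule. Two SAP bullets count unique TEAEs, which hints at de-duplication. That is possible, but the term is undefined and is absent from the Day 15 bullets. If a rule exists elsewhere, the SAP should state it.

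Stronger readings are tempting and do not stand:

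- A reader might infer that an event present before dosing becomes a TEAE when it eases. The TEAE definition admits existing events only if they worsened. The missing linking rule leaves room for a programming slip, but the text does not call for that result.
- A reader might infer that every grade change after Day 15 is spurious. A mild event from Day 5 that becomes severe on Day 60 is relevant to longer dosing. Assigning each linked event its first onset date and worst severity would hide it in the early table.
- A reader might infer that full N is the wrong denominator. For any event with onset after Day 15 it is defensible. Events are collected to the follow-up contact, most early stoppers are seen 30 to 37 days after the last dose (not those who withdraw consent or are lost), and full N keeps the randomised comparison. It falls short only as a description of risk during dosing beyond Day 15.
- A reader might infer a known bias for or against omadacycline. The documents give no early-stopping or grade-change rates by arm. Grade-change records raise the late rate and early stopping lowers it, so the net direction is unknown.

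The partial-date problem is real but should affect few events: the protocol requires adverse events to be fully characterised and queries resolved before lock. The SAP also does not say that imputed dates drive the Day 15 split.

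**Conclusion.** The point holds for decreases in severity. Read together, Protocol 8.19.3 and SAP 13.2 count an event that starts by Day 15 and only eases afterwards as a late-onset TEAE. That overstates late onset in the one adverse event split covering dosing beyond 14 days.

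The size cannot be known from the documents. Under the assumed ranges it is at most about 1 to 15 percentage points of an arm for a given preferred term. The conclusion assumes that sites follow the recording rule and that no linking rule sits in the unseen specifications.

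The documents do not support extending this to the other safety tables as a whole. Overall subject incidence by preferred term and the highest-severity table do not depend on the Day 15 split, and by-subject listings would let a reviewer trace individual cases. The denominator and partial-date matters are refinements, not errors of the same standing.

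**What to change.** Amend SAP section 13.2 as follows.

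(a) Link consecutive records of the same continuing event. A record that is only a decrease in severity creates neither a TEAE nor an after-Day-15 onset. An increase in severity after Day 15 stays in the after-Day-15 table, on a separate line as late worsening of an earlier event.

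(b) Keep the full-N table. Add a supplementary version limited, in numerator and denominator alike, to subjects still receiving test article after Day 15, with that n shown by arm. Its drawback is that it conditions on a post-randomisation event that tolerability may influence, so label it descriptive only.

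(c) Minor: where a partial onset date is compatible with both periods, show the event as undetermined instead of letting the imputed date place it in the early table.

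The cost is SAP wording and programming: a linking variable, or a rule based on the same preferred term with contiguous dates, plus the last-administration date that SAP section 13.1 already uses. A contiguous-date rule will need manual review where dates are incomplete. If the blind has already been broken, SAP section 6 requires the added outputs to be labelled post hoc.

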13.3 Clinical Laboratory Evaluation

Laboratory parameters (serum chemistry, hematology, and coagulation) will be summarized using descriptive statistics at baseline and at each post-baseline time point (the Day 28 and 84 visit, Day84/EOT) and for the most extreme (high and/or low) post-baseline value at any visit (including unscheduled results). Changes from baseline will also be summarized.

Select laboratory parameters will be graded according to the Division of Microbiology and Infectious Diseases (DMID) grading criteria, version 5.0. Incidence of potentially clinically significant (PCS) events (at least a 2-grade increase from baseline) will be presented by time point and for the most extreme post-baseline value at any visit (including unscheduled results).

The number and percentage (based on the number of subjects with a normal level at baseline) of subjects in each treatment group with an elevated transaminase (AST or ALT) level ($> 3 \times$ upper limit of normal [ULN], $> 5 \times$ ULN, and $> 10 \times$ ULN), an elevated bilirubin level ($> 1.5 \times$ ULN and $> 2 \times$ ULN) will be presented by study visit and at any post-baseline visit. A listing of subjects who meet the laboratory criteria for Hy's law at the same visit will also be provided. The laboratory criteria for Hy's law are defined as 1) ALT or AST $> 3 \times$ ULN, ALP $\leq 2.0 \times$ ULN, and total bilirubin > 1.5 ULN and 2) ALT or AST $> 3 \times$ ULN, ALP $\leq 2.0 \times$ ULN, and total bilirubin $> 2 \times$ ULN.

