6.3 Exclusion Criteria

Subjects meeting any of the following criteria at Screening and/or Baseline will be excluded from participation in the study:

1. Pregnant or nursing (breastfeeding) women.
2. Has received antibiotic treatment within 6 months prior to Screening for MABC or MAC.
3. Has received systemic or inhaled antibiotic therapy (other than chronic macrolide therapy) within 4 weeks prior to Screening.
4. Is experiencing an exacerbation of an infection with a non-*Mycobacterium* species (eg, *Pseudomonas aeruginosa*) that the investigator considers clinically relevant.
5. Has any of the following medical conditions:
 - Active pulmonary malignancy (primary or metastatic), or any type of malignancy requiring chemotherapy or radiation within 1 year prior to Screening.
 - Active allergic bronchopulmonary mycosis, or any other condition requiring chronic treatment with systemic corticosteroids (ie, prednisone dose \geq 15 mg/day for a period of \geq 4 consecutive weeks above this level; see [Appendix 2](#)) within 90 days prior to Screening.
 - Radiologic evidence of cavitary disease.
 - Known active pulmonary tuberculosis.
 - Cystic fibrosis.
 - History of lung transplantation.
 - Another advanced lung disease with a known percent predicted forced expiratory volume in 1 second $<$ 30%.
 - Disseminated or extra-pulmonary NTM disease.
6. Screening calculated creatinine clearance $<$ 30 mL/minute, using the Cockcroft-Gault equation ([Appendix 2](#)), requirement for any form of dialysis (eg, hemodialysis, peritoneal dialysis), or other evidence of severe renal disease.
7. Has any of the following at Screening:
 - Alanine aminotransferase or aspartate aminotransferase \geq 3 \times upper limit of normal.
 - Total bilirubin $>$ 1.5 \times upper limit of normal.
 - Suspected or confirmed clinical evidence of end-stage liver disease (eg, ascites, hepatic encephalopathy).
8. History of having experienced unstable cardiac disease (eg, unstable angina, myocardial infarction, acute congestive heart failure, unstable cardiac arrhythmia, etc.) within the 3 months prior to Screening.
9. Significant immunological disease determined by any of the following:
 - Current or anticipated neutropenia defined as $<$ 500 neutrophils/mm³.
 - Known infection with human immunodeficiency virus (HIV).

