APPENDIX D: DMID ADULT TOXICITY TABLE

The DMID Adult Toxicity Table (21-NOV-2007) was modified to exclude the clinical component of the toxicity grading because clinical signs and symptoms related to abnormal laboratory values are not collected in this study. In addition, Grade 0 was added to the table so that shifts from normal could be analyzed. Grades for enzymes were modified as indicated in the table below.

For toxicity grades based on a multiple of the ULN, the normal range from the central laboratory will be applied.

For toxicity grades based on fixed values, the grades will be assigned regardless of the normal actual range values from the central laboratory. For example, a hemoglobin value of 10.0 gm/dL will be assigned a grade of 1 toxicity, even if the lower limit of normal from the laboratory was 9.8 gm/dL.

HEMATOLOGY					
	Grade 0	Grade 1	Grade 2	Grade 3	Grade 4
Hemoglobin (gm/dL)	> 10.5	9.5-10.5	8.0-9.4	6.5-7.9	< 6.5
Absolute Neutrophil Count (count/mm ³)	> 1500	1000-1500	750-999	500-749	< 500
Platelets (count/mm ³)	≥ 100,000	75,000-99,999	50,000-74,999	20,000-49,999	< 20,000
WBCs (count/mm ³)	1000-10,999	11,000-12,999	13,000-14,999	15,000-30,000	> 30,000 or < 1,000

CHEMISTRY

	Grade 0	Grade 1	Grade 2	Grade 3	Grade 4
Hyponatremia (mEq/L)	> 135	130-135	123-129	116-122	< 116
Hypernatremia (mEq/L)	< 146	146-150	151-157	158-165	> 165
Hypokalemia (mEq/L)	> 3.4	3.0-3.4	2.5-2.9	2.0-2.4	< 2.0
Hyperkalemia (mEq/L)	< 5.6	5.6-6.0	6.1-6.5	6.6-7.0	> 7.0
Hypocalcemia (mg/dL) (corrected for albumin)	> 8.4	8.4-7.8	7.7-7.0	6.9-6.1	< 6.1
Hypercalcemia (mg/dL) (correct for albumin)	≤ 10.5	10.6-11.5	11.6-12.5	12.6-13.5	> 13.5
Hypomagnesemia (mEq/L)	> 1.4	1.4- 1.2	1.1-0.9	0.8-0.6	< 0.6
Hypophosphatemia (mg/dL)	≥ 2.5	2.0-2.4	1.5-1.9	1.0-1.4	< 1.0
Hyperbilirubinemia (total bilirubin)	< 1.1×ULN	1.1-1.5×ULN	> 1.5- 2.5×ULN	> 2.5-5×ULN	> 5×ULN
	< 1.1×ULN	1.1-1.5×ULN	> 1.5- 3.0×ULN	> 3.0-6×ULN	> 6×ULN

ENZYMES

	Grade 0	Grade 1	Grade 2	Grade 3	Grade 4
AST (SGOT)	< 1.25×ULN	1.25-2.5×ULN	> 2.5-5×ULN	> 5-10×ULN	> 10×ULN
ALT (SGPT)	< 1.25×ULN	1.25-2.5×ULN	> 2.5-5×ULN	> 5-10×ULN	> 10×ULN
GGT	< 1.25×ULN	1.25-2.5×ULN	> 2.5-5×ULN	> 5-10×ULN	> 10×ULN
Alkaline Phosphatase	< 1.25×ULN	1.25-2.5×ULN	> 2.5-5×ULN	> 5-10×ULN	> 10×ULN
Lipase	< 1.1×ULN	1.1-1.5×ULN	> 1.5-2.0×ULN	> 2.0-5.0×ULN	> 5.0×ULN

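### Some raised-baseline subjects whose ALT, AST or bilirubin crosses a liver threshold are counted in neither laboratory incidence table

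*SAP*

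**What the plan says.** Three parts of the plan bear on this.

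- **Threshold table (SAP 13.3).** Counts are shown alongside the "percentage (based on the number of subjects with a normal level at baseline) of subjects in each treatment group with an elevated transaminase"; the cut-offs are 3, 5 and 10 times ULN, reported by visit and at any post-baseline visit. The same sentence covers bilirubin above 1.5 and 2 times ULN.
- **Potentially clinically significant (PCS) table (SAP 13.3, Appendix D).** "Incidence of potentially clinically significant (PCS) events (at least a 2-grade increase from baseline) will be presented". This is done for each visit and for the worst result after baseline, with no condition on baseline. The grades come from Appendix D, which notes: "Grades for enzymes were modified as indicated in the table below".
- **Entry limits (Protocol 6.3, exclusion 7).** "Alanine aminotransferase or aspartate aminotransferase" at or above 3 times ULN at Screening excludes a subject, as does total bilirubin above 1.5 times ULN. Moderately raised values are therefore allowed in.

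SAP 13.3 also plans descriptive statistics by visit and for the most extreme post-baseline value, changes from baseline, and a Hy's law listing. None of these is limited to subjects normal at baseline.

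**The concern.** Subjects who enter with raised liver tests are outside the base of the threshold table. One would expect the PCS table to pick them up. But the Appendix D grades are wide, and a two-grade rise from a baseline already at grade 1 or 2 demands a high value. A subject can cross 3 times ULN, and in one band 5 times ULN, without qualifying.

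Safety is a primary objective, and the incidence of PCS laboratory values is one of its listed endpoints (Protocol 4). Protocol 3.2 describes this as the first clinical trial to give omadacycline for longer than 14 days, and no data monitoring committee is planned (Protocol 12.7). The end-of-study liver tables therefore carry much of the weight, and a between-arm count that omits part of the raised-baseline group is incomplete.

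**Working it through.** The plan states no figure here to reproduce. The check applies the plan's own cut-offs to every above-normal baseline that the entry limits permit. All values are multiples of ULN, and normal is taken as at or below 1.

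**Inputs**
- ALT/AST grades (SAP Appendix D): grade 0 <1.25; 1 = 1.25–2.5; 2 = >2.5–5; 3 = >5–10; 4 = >10.
- Bilirubin grades (SAP Appendix D, two rows): grade 0 <1.1 and grade 1 = 1.1–1.5 in both. Row 1: 2 = >1.5–2.5; 3 = >2.5–5; 4 = >5. Row 2: 2 = >1.5–3.0; 3 = >3.0–6; 4 = >6. The text as supplied does not show when each row applies, so both are used.
- Above-normal baselines within the entry limits (Protocol 6.3): ALT/AST >1 to <3; bilirubin >1 to 1.5.

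**Rule.** PCS is met when grade(post-baseline) − grade(baseline) ≥ 2. A value falls in the gap if baseline is above normal, the value exceeds a threshold in SAP 13.3, and PCS is not met.

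| Test | Baseline | Grade | PCS needs | Counted in neither table |
|---|---|---|---|---|
| ALT/AST | >1 to <1.25 | 0 | grade 2: >2.5 | none |
| ALT/AST | 1.25–2.5 | 1 | grade 3: >5 | >3 to 5 |
| ALT/AST | >2.5 to <3 | 2 | grade 4: >10 | >3 to 10 |
| Bilirubin | >1 to <1.1 | 0 | grade 2: >1.5 | none |
| Bilirubin | 1.1–1.5 | 1 | grade 3: >2.5 (row 1) or >3.0 (row 2) | >1.5 to 2.5, or to 3.0 |

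**Largest uncounted rises**
- ALT/AST from grade 1: 5 / 1.25 = 4.0-fold.
- ALT/AST from grade 2: 10 / 2.51 = 3.98-fold.
- Bilirubin: 2.5 / 1.1 = 2.3-fold (row 1) or 3.0 / 1.1 = 2.7-fold (row 2). The gap includes values above 2 times ULN.

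**Normal baselines, for comparison.** A normal value is grade 0. ALT/AST above 3, or bilirubin above 1.5, is at least grade 2, so PCS always fires. The two tables overlap for normal-baseline subjects and leave the gap among the others.

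**How many subjects.** The documents give no prevalence of raised baselines. If 1%, 5% or 10% of the 75 planned subjects had a baseline in a gap band, that would be 0.75, 3.75 or 7.5 subjects, before asking whether any of them had a rise. One uncounted subject is 1/45 = 2.2% of the omadacycline arm or 1/30 = 3.3% of the placebo arm.

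**The case against.** A reader might infer that large rises in these subjects appear in no safety output. The documents do not support that. The values enter the most-extreme-value and change-from-baseline summaries without restriction. SAP 6 includes the maximum in continuous summaries, and SAP Appendix E takes the highest ALT, AST and bilirubin as the worst. An ALT going from 2.6 to 9.9 times ULN could well set the reported maximum. By-subject listings carry the data (SAP 6), Hy's law cases are listed whatever the baseline, and clinically significant abnormalities may be recorded as adverse events (Protocol 8.19.4).

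Nor does the PCS rule miss all raised-baseline subjects. It catches every threshold crossing from an ALT/AST baseline below 1.25 or a bilirubin baseline below 1.1 times ULN, every ALT/AST value above 5 from a grade 1 baseline, and every ALT/AST value above 10 from any baseline within the entry limits.

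It is also fair to say that the parenthesis in SAP 13.3 literally defines the percentage base. It does not say that the count is restricted too, and the table shells are in a separate document. A normal-at-baseline analysis is itself a sensible way to isolate newly emergent elevation.

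These points narrow the concern without removing it. A maximum shows one extreme per arm and does not say how many subjects crossed a threshold. Listings are not a comparison by arm. The Hy's law listing also needs raised bilirubin, so an isolated transaminase rise is absent. Protocol 8.19.4 judges laboratory events against what is expected from the subject's baseline, which may make recording less likely when baseline is already raised. If only the denominator is restricted, the count and its base come from different groups and the percentage is hard to interpret. Either reading needs an edit.

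**Conclusion.** The point holds in a limited form. If the numerator is restricted along with the denominator, which is the natural but unstated reading, the three bands in the table above are counted in neither laboratory incidence table. If it is not restricted, the subjects are counted but the percentage mixes two populations.

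The gap is confined to those bands. From a baseline within the entry limits, ALT/AST above 5 times ULN escapes only when baseline was >2.5 to <3, and no value above 10 escapes. The number of subjects affected is unknown and could be zero; the percentages in the working are assumptions.

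One further assumption is that baseline respects the entry limits. They apply at Screening, up to 56 days before dosing, whereas SAP 11.2 takes the last value before the first dose. A higher baseline is therefore possible, and from ALT/AST above 5 (grade 3) a two-grade rise cannot occur.

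This is a cheap improvement to a primary safety summary. It does not show that liver signals would go unseen.

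**What to change.** In SAP 13.3, present the threshold counts and percentages for all safety subjects with a post-baseline value, split into baseline normal and baseline above normal, with numerator and denominator from the same group in each block. State what counts as normal, and when each Appendix D bilirubin row applies if the SAP does not already label the rows. The sponsor's normal-at-baseline view stays as one of the blocks. A count of subjects exceeding a chosen multiple of their own baseline is an optional addition for the above-normal group; the documents offer no basis for a particular multiple.

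The cost is one SAP sentence and one extra table block. No new data are needed, and conduct and subject management do not change. The downside is small cell counts in the above-normal block, so it should be read as counts more than as rates. If the blind has already been broken, SAP 6 requires the added block to be labelled post hoc.
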